## 11.0 STATISTICAL/ANALYTICAL ISSUES

### 11.1 Handling of Dropouts or Missing Data

Number of missing values will be summarized and reported as appropriate.

[REDACTED]

Impact of missing data on the primary analysis for Week 12 endpoints will be evaluated by performing sensitivity analysis based on the observed cases in the ITT population.

[REDACTED]

All other effectiveness endpoints will be evaluated based on the observed cases in ITT, i.e. no imputations will be done.

If the adverse event start date is missing, it will be assumed that the AE started on the day of the most recent treatment. Missing stop date for adverse event will not be imputed.

If the adverse event severity assessment is missing, the highest level of severity will be assumed. Missing relationships in adverse event will be imputed as related. AEs will be considered as serious if the assessment on whether the AE is serious or not is missing.

The observed cases in the Safety population will be used for all other safety analysis.

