The number of subjects with AEs unrelated to both study product and injection procedure as well as the number of events will be summarized by SOC, PT, and severity.

In addition, for related AEs, the number of days to onset and the duration of event will be summarized by SOC and PT using mean, SD, min, max and median.

Time to onset of an AE will be derived as the start date minus the date of most recent treatment. If the start date is missing, it will be assumed that the AE started on the day of most recent treatment.

Duration of an AE will be derived as the stop date minus the start date + 1. If the start date is missing, it will be assumed that the AE started on the day of most recent treatment. Missing stop date will not be imputed and therefore no duration will be calculated in these cases. Instead, the number of AEs that were ongoing at the end of the study will be given.

If a subject has more than 1 AE of the same PT and there are different grades of severity, only the highest grade will be represented in the summary of severity.

Action taken for related AEs will also be summarized.

To evaluate consistency of the results across different subgroups, AEs will also be analyzed across different subgroups as described in the exploratory objectives (see Section 3.1.4) using a table with related AEs by SOC, PT and severity.

Hypertrophic scarring/hyperpigmented scarring will be summarized by FST I-III, IV, and V-VI.

Incidences of visual disturbances are considered Adverse Events of Special Interest (AESIs) and include but are not limited to the following: loss of vision, blurry vision, double vision, pain in or around the eye, blind spot or shadow in the visual field, trouble moving eyes, etc.

All reported AEs will be listed in data listings including time to onset, duration of AE and timing of the AE. Timing would be the variable indicating whether the AE occurred after no treatment, initial treatment, or optional retreatment.

By-subject listings also will be provided for all subjects (safety population) for the following: AEs related to study product or injection procedure, AEs resulting in discontinuation of study product, serious AEs, and AESIs. Adverse events with late onset (onset >21 days) will be provided in a listing.

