## 15.0 TABLES AND LISTING CONVENTIONS

Mock-ups for statistical tables and listings will be provided. Final formats for the statistical tables and listings may deviate from these mock-ups upon agreement with Galderma. Footnotes will be used as needed to clarify the information that is presented in the tables and listings. Unless otherwise requested by Galderma, the term 'subject' will be used in all tables and listings, in accordance with Clinical Data Interchange Standards Consortium (CDISC) standards.

All tables and listings will use landscape orientation. Margins will be at least 2.0 cm at the top and bottom and at least 0.8 cm on the left and right, excluding headers and footers, in accordance with electronic Common Technical Documents (eCTD) guidelines. Font will be Courier New, unless otherwise specified, with a 10-point font size in most cases. Page numbering will be sequential within each table, listing, and figure. Column headers should be in initial capital letters. Units for numeric data will be included when appropriate.

Tables and data listings will be created from different SAS programs. A single program may produce multiple tables or multiple data listings from the same dataset (e.g., all clinical chemistry data listings may be generated by a single program).

The general layout of tables and listings will be as follows:

Galderma Research and Development, LLC

Page x of y

Protocol: 43USCH1702

Run Date: DDMMYY HH:MM

Clinical Study Report

Listing 16.2\_x (or Table 14.x\_x)

<Title>

<Population>

---

Col 1      Col 2      Col 3      Etc.

---

<Any footnotes>

File Name: <pathname for SAS program>

Mock-ups for statistical tables will include headers, title numbers, titles, column headers and footers, and a proposed layout for the display of data. The final decision on the precision (i.e., number of decimal places) for presentation of descriptive statistics will be made by Galderma after review of draft statistical tables and before database freeze.

Mock-ups for data listings will include headers, title numbers, titles, column headers, and footers. Data listings will provide all data either collected on the corresponding eCRF page or loaded directly into the database, unless otherwise indicated. If there are too many fields to be fit into a single page, data should be grouped logically and the listings will be generated as Part I, Part II, etc.

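### A missing AE start date becomes a time to onset of 0 days, which enters the onset statistics, bars the AE from the >21-day listing and maximises its duration

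*SAP*

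**What the plan says.** SAP 11.1 deals with an AE that has no start date: "it will be assumed that the AE started on the day of the most recent treatment". SAP 13.1 repeats the rule for both derived quantities, time to onset and duration: "If the start date is missing, it will be assumed that the AE started on the day of most recent treatment". Time to onset is the start date minus the most recent treatment date. Duration is the stop date minus the start date, plus 1.

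Three displays use these quantities:

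- A summary confined to AEs counted as related: "the number of days to onset and the duration of event will be summarized by SOC and PT using mean, SD, min, max and median".
- "Adverse events with late onset (onset >21 days) will be provided in a listing". This sentence is not limited to related AEs.
- "All reported AEs will be listed in data listings including time to onset, duration of AE and timing of the AE".

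For stop dates, SAP 13.1 says "Missing stop date will not be imputed and therefore no duration will be calculated in these cases", followed by "Instead, the number of AEs that were ongoing at the end of the study will be given".

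SAP 11.1 fills other gaps in the cautious direction: missing severity takes the highest grade, missing relationship becomes related, and missing seriousness becomes serious. An AE with no recorded relationship therefore also enters the related-AE onset and duration summary.

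**The concern.** One imputation serves two purposes. Placing an undated AE on the treatment day is cautious when the question is whether treatment caused it, and it is needed to allocate the AE to the initial or the retreatment period. When the question is how late reactions appear, the same rule reports an unknown onset as an immediate one. That runs against the direction of the other AE imputations in SAP 11.1.

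The onset summary and the late-onset listing are where a reader would look for delayed reactions to a filler. Such reactions may be few, so a single AE missing from that listing could matter to that reader even though it changes no test.

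**Working it through.** The documents give no figure to reproduce. The check applies the SAP's own definitions. Let T be the most recent treatment date, s the true but unrecorded start date (on or after T), and S the stop date if there is one.

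**1. Time to onset.** The imputed start is T, so onset = T − T = 0 days, whatever s was. This is a difference in days, not a study day; SAP 4.0 has no Day 0.

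**2. Onset statistics (related AEs, by SOC/PT).** Suppose a row has n AEs, of which k have an imputed start.
- Reported mean = [(n − k) × (mean of recorded onsets) + k × 0] / n = ((n − k)/n) × (mean of recorded onsets).
- Shortfall against the true mean = (sum of the k true onsets) / n. It is zero only if all k AEs truly began on the treatment day, and it is never negative.
- The minimum becomes 0 whenever k ≥ 1. This changes nothing in a row that already holds a same-day event.
- The median and SD are computed with k artificial zeros included.

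The documents give neither k nor n, so no percentage is put on this.

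**3. Late-onset listing.** The criterion is onset > 21 days. With onset = 0, 0 > 21 is false, so the AE is not listed. This holds for every AE with a missing start date.

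Other recorded dates can carry information that the rule ignores. Protocol 8.1 has subjects asked at each visit about problems since the previous one. A first report at a late visit, after a visit with nothing reported, would suggest late onset. Protocol 8.6.3 words the question differently, as since receiving treatment, so this information will not always exist.

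**4. Duration.** With the imputed start, duration = S − T + 1. With the true start it is S − s + 1. Since s ≥ T, the reported value is at least the true one, by s − T days. It is the longest duration that measurement from that treatment allows. A late, short AE with a known stop date would be summarised as an immediate, long one.

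**5. What the full listing shows.** SAP 15.0 says: "Data listings will provide all data either collected on the corresponding eCRF page or loaded directly into the database, unless otherwise indicated". Unless the listing is specified otherwise, the blank start date therefore appears. SAP 13.1 also puts derived time to onset in that listing, so a 0 would stand beside the blank. The readable text states no marker for an imputed onset.

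**The case against.** The strongest reply is that this is a disclosed convention, applied consistently in SAP 11.1 and 13.1 and cautious for attribution. Few AEs should be affected. Protocol 8.6.3 requires start and stop dates, Protocol 9.1 provides logical checks and manual review, and Protocol 9.2.2 has monitors review completeness and raise queries. Every AE stays in the full listing, where a blank date is likely to be visible. All of this stands and keeps the point minor. It does not answer the point itself: when the rule is used, an unknown onset is summarised as 0, and nothing in the late-onset listing tells its reader to look elsewhere.

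A reader might infer more than the documents support:

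- *That AEs are hidden.* They are not. They are absent only from the late-onset listing.
- *That imputed dates will go unmarked.* This cannot be asserted. Table and listing mock-ups are not available, and parts of SAP 11.1 are redacted.
- *That the duration table conceals persistent AEs.* The SAP says openly that no duration is calculated without a stop date, and gives the number ongoing instead. Whether that number is given by SOC/PT is not stated, and silence does not show that it is not. Related AEs ongoing at completion are followed further (Protocol Synopsis, Evaluation of safety). Protocol 8.6.8, which covers that follow-up, is not readable, so it is unknown whether later stop dates enter the table. The start-date rule lengthens durations, so the duration summary is not biased in one direction only.

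**Conclusion.** The point holds as a low-priority correction. Under the stated rule, an AE with a missing start date always has onset 0. If related, it adds an artificial 0 to the onset statistics. Related or not, it can never enter the >21-day listing. With a stop date, it receives the maximum duration from that treatment. These results follow from the definitions and need no assumption beyond onset on or after the treatment used.

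The size cannot be computed, because the documents give no rate of missing start dates; the data checks suggest that it is small. The effect is confined to descriptive safety displays and alters no hypothesis test, endpoint or primary conclusion. The conclusion rests on the readable text, and redacted passages could contain a further rule.

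On stop dates there is only a small gap. A missing stop date is not the same as an ongoing AE. One recorded as recovered (an outcome that Protocol 8.6.3 allows) but without a stop date has no duration and would not belong in the ongoing count.

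**What to change.** Keep the imputation for attribution and for allocating AEs to the initial or retreatment period. For the displays, add to SAP 13.1:

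- (a) Exclude AEs with an imputed start date from both the time-to-onset and the duration statistics, and report how many were excluded.
- (b) Include AEs with a missing start date in the late-onset listing, flagged 'onset unknown', unless known dates rule out onset later than 21 days.

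A minor addition is to label the duration summary 'AEs with known start and stop dates'. Beside the ongoing count already planned, show elapsed time to last contact, and give separately the number of AEs recorded as recovered with no stop date.

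The cost is a few lines of SAP text and program code, using fields already collected (start date, stop date, outcome, visit dates). The downside is a slightly longer late-onset listing and a few extra table columns.

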### 13.2 Pre-defined, expected, post-treatment events

[REDACTED]

[REDACTED]

Diary data will be counted and displayed separately from other AE data.

Number and percentage of subjects reporting each pre-defined, expected, post-treatment symptoms, [REDACTED] will be presented by treatment, type of event and maximum severity. Number of days with the event will be summarized by treatment [REDACTED]

[REDACTED]

[REDACTED]

[REDACTED]

[REDACTED]

*Effective*

Version: 1.0

*Effective*

Version: 1.0

### 13.10 Laboratory Assessments

For all women of childbearing potential, a urine pregnancy test will be performed at screening and all injection visits prior to treatment.

The pregnancy test data will be presented by treatment and subject in data listing.

### 13.12 Concomitant Medications and Concomitant Procedures/Treatments

The number and percentage of subjects reporting concomitant medications will be summarized by treatment.

In addition, the number and percent of subjects reporting concomitant medication, and the number of drugs (total number and the number of ongoing drugs), will be summarized by reason.

The same summary will be done for concomitant procedures/treatments.

Also, the number and percentage of the subjects who took each medication will be tabulated by WHO Drug Dictionary Anatomical Therapeutic Chemical 3rd level (ATC-3) and preferred name for concomitant medications. This table will include only those medications that are taken by >2% of the subjects. If the 3rd level term is not available, the next available level (e.g., ATC-2) will be used. A subject will only be counted once within each ATC-3 code and within each preferred name.

Concomitant medications that started due to an AE will be summarized separately.

All concomitant medication and concomitant procedures/treatments data will be presented by treatment and subject in a data listing.

## 14.0 QUALITY CONTROL

All data displays and analyses will adhere to the International Conference on Harmonisation (ICH) Harmonized Tripartite Guideline: Structure and Content of Clinical Study Reports (ICH Topic E3).

All analyses will be performed using SAS® Version 9.4 (or later). Advanced Clinical will follow its standard operating procedures in the creation and quality control of all tables, listings, figures, and analyses. Galderma or its designee will review all tables, listings, and figures prior to final database lock. All final SAS programs and associated output files will be transferred to Galderma in agreed-upon format at project completion.

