10.9 Withdrawals and deviations

All withdrawn subjects will be listed individually, including at least subject number, date and reason for withdrawal, and last visit performed.

Subjects with protocol deviations will be listed individually, including subject number and observed deviation. Depending on the seriousness of the deviation, subject might be excluded from the PP population, which should be documented prior to database lock.

Deviations from the statistical plan will be documented CSR.

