## 4.0 GENERAL ANALYSIS CONVENTION

Data collected in this study will be documented using summary tables and subject data listings. Continuous endpoints will be summarized using descriptive statistics, e.g. number of subjects, mean, median, standard deviation, minimum and maximum values. Categorical endpoints will be presented in frequency tables with number and percentage of observations for each level.

Group A and Group B will be analyzed and presented separately. Data will be summarized by treatment group in Group A and by injection tool (Needle/Cannula) in Group B.

Confidence intervals will be two-sided and constructed at a confidence level of 95%.

Study days will be calculated relative to the date of first dose of study product. Day 1 will be the first day of study product administration in the study. The day prior to Day 1 will be Day -1. There will be no Day 0.

Baseline will be the last assessment prior to the first dose of study product.

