## 5.0 ANALYSIS POPULATIONS

The Analysis Populations are defined separately for Group A and Group B as described below.

- **Safety Population:** Includes all subjects who were injected at least once. Subjects are analysed according to the treatment they actually received.

- **Intention-to-Treat (ITT) Population:** Includes all subjects who were randomized. Subjects are analysed according to the treatment they were randomized to.
- **Per-Protocol (PP) Population:** Includes all subjects in ITT who complete the Week 12 visit without any deviations considered to have substantial impact on the primary effectiveness outcome.

Safety population will be the basis for all safety evaluations. When performing effectiveness analysis, the ITT population will be used. Primary effectiveness analysis will be repeated using the PP populations. Additional endpoints maybe explored in the PP population if deemed necessary.

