## 7.0 PROTOCOL DEVIATIONS

Protocol deviations will be presented by subject in a data listing. Subjects with protocol deviations will be listed individually, including subject number and observed deviation. Number and percentage of subjects with each type of protocol deviation will be summarized by site for individual treatment group and overall, as appropriate, for the ITT population.

Depending on the seriousness of the deviation, subject might be excluded from the PP population, which shall be documented prior to database lock. [REDACTED]

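### Could Group A per-protocol exclusions be settled after the sponsor has seen draft results by arm?

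*SAP*

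**What the plan says.** Two steps run up to the end of data handling.

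- **Output review.** Under SAP 14.0, "Galderma or its designee will review all tables, listings, and figures prior to final database lock". SAP 15.0 adds that the decision on the number of decimal places will be "made by Galderma after review of draft statistical tables and before database freeze".
- **PP membership.** SAP 5.0 defines the PP population as ITT subjects who complete the Week 12 visit "without any deviations considered to have substantial impact on the primary effectiveness outcome". SAP 7.0 states: "Depending on the seriousness of the deviation, subject might be excluded from the PP population, which shall be documented prior to database lock". Protocol 10.9 gives the same rule and the same deadline.

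On layout, SAP 4.0 says "Data will be summarized by treatment group in Group A and by injection tool (Needle/Cannula) in Group B", and SAP 7.0 applies this to deviations: "Number and percentage of subjects with each type of protocol deviation will be summarized by site for individual treatment group and overall".

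On the weight of the two populations, SAP 5.0 says "When performing effectiveness analysis, the ITT population will be used", with the primary analysis repeated in PP. SAP 11.1 adds an observed-case sensitivity analysis in ITT. Protocol 9.1 has the statistical analyses generated from locked datasets.

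**The concern.** PP exclusion is discretionary: a subject might be excluded, depending on how serious a deviation is judged to be, and no list of qualifying deviations is visible. If the people making that judgement have already seen Week 12 results or deviations by arm, the choice can be influenced by its effect on the result. In a non-inferiority trial the PP repeat is read as a check that deviations have not blurred a real difference, and it can do that only if its membership was fixed without knowledge of the results.

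The visible blinding text does not remove the worry. Protocol 4.4.2 blinds the evaluator, leaves the treating investigator and safety assessors unblinded, and says nothing visible about sponsor staff or the statistician. At stake is the credibility of the Group A PP repeat.

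**Working it through.** **Order of events**

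| Step | Where | Deadline | Treatment codes |
|---|---|---|---|
| Sponsor reviews outputs | SAP 14.0 | final database lock | not stated |
| Sponsor settles decimal places from draft tables | SAP 15.0 | database freeze | not stated |
| PP exclusions documented | SAP 7.0, protocol 10.9 | database lock | not stated |
| Statistical analyses generated | protocol 9.1 | after lock | true codes, by implication |

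Three things follow.

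1. The visible text does not put the PP decision before the output review, nor does it put it after. The three deadlines use three terms with no visible definitions.
2. SAP 4.0 and 7.0 describe table columns. A run on a dummy randomisation list has the same columns, so a by-arm layout does not show that true codes are used.
3. SAP 14.0 and protocol 9.1 are compatible if the outputs reviewed before lock are drafts and the final outputs are rerun on locked data.

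**Size, if the worst order did occur**

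Inputs from the documents: 210 randomised 2:1, about 140 to GAL1704 and 70 to the comparator (SAP 3.3); about 12% drop-outs and non-evaluable subjects (SAP 3.4); margin 0.5, judged by the upper confidence limit (SAP 10.1); two-sided 95% intervals (SAP 4.0).

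Assumptions: SD 0.6 to 1.0; the 12% loss equal in both arms; k GAL1704 subjects excluded by choice, averaging d units worse than their arm mean; no selective exclusion in the comparator arm.

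- Expected loss: 210 × 0.12 = 25.2 subjects, drop-outs included.
- PP size: 140 × 0.88 = 123.2 and 70 × 0.88 = 61.6, taken as 123 and 62.
- Shift in the difference = k × d / 123.
- SE = SD × √(1/123 + 1/62) = SD × 0.1558, that is 0.0935, 0.1246 and 0.1558 for SD 0.6, 0.8 and 1.0. The 95% half-widths (1.96 × SE) are 0.183, 0.244 and 0.305.
- Chance that the PP repeat shows non-inferiority at a true difference of 0.5 = Φ(−1.96 + shift/SE), which is 2.5% with no shift.

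| k, d | Shift | % of margin | SD 0.6 | SD 0.8 | SD 1.0 |
|---|---|---|---|---|---|
| 2, 0.5 | 0.008 | 1.6% | 3.1% | 2.9% | 2.8% |
| 5, 1 | 0.041 | 8.1% | 6.4% | 5.1% | 4.5% |
| 8, 1 | 0.065 | 13.0% | 10.3% | 7.5% | 6.1% |

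Example: 0.0650/0.0935 = 0.695, and Φ(−1.96 + 0.695) = 10.3%.

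**How reachable is the top of that table?** Going from 140 to 123 loses 17 GAL1704 subjects in all, so k = 8 is nearly half of them, before any drop-outs are counted. With SD 0.6, d = 1 means exclusions averaging 1/0.6 = 1.67 SD worse than the arm. If deviations are unrelated to outcome and the worst 8 of 17 deviating subjects were picked, simulation puts their average at 0.81 SD. The shift is then 8 × 0.81/123 = 0.053 SD, shift/SE = 0.053/0.1558 = 0.34, and the chance is about 5.2% whatever the SD. Exclusions unrelated to outcome give no bias.

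**The case for a change.** The case for acting is a fair one. Choosing decimal places from draft tables suggests tables filled with data, since SAP 15.0 treats mock-ups separately. No visible text masks the sponsor, and reports of adverse events of special interest sent to the sponsor name the product injected (protocol 8.6.5). The primary objective is non-inferiority, the plan itself chose to repeat the analysis in PP, and SAP 5.0 leaves room for further endpoints in that population. A sentence requiring dummy codes and an earlier PP sign-off would cost little.

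What stands is that the visible text does not force the safe order. The rest does not carry it to a fault in the plan:

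- Drafts filled with data are not the same as drafts with true codes.
- The sentence directly after the PP rule in SAP 7.0 is blacked out, as is part of protocol 4.4.2, and protocol 10.1 and 10.2 are not visible. These are natural places for a masking or sign-off rule, and redacted text cannot be counted as absent.
- The reviews cited are for quality control and formatting. The sample layout in SAP 15.0 carries another study's number (43USCH1702), which suggests template wording and makes it weak evidence of this study's sequence.
- Discretion is bounded. Completing Week 12 is objective, and deviations are reported in the eCRF and verified by the monitor (protocol 12.1), so only a subject with a recorded deviation can be excluded on this ground.

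**Conclusion.** This is a gap in procedural detail that analysts fill sensibly, and no change to the plan is needed. Draft outputs on dummy codes, a PP list signed before any treatment-labelled output is released, and a final run on locked data would satisfy every visible sentence in both documents.

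ITT membership is fixed by randomisation, ITT is the basis for the effectiveness analysis, and no visible decision rule uses the PP result. The non-inferiority conclusion therefore does not depend on how the gap is filled. The 2.8% to 10.3% range describes only the supportive Group A repeat. It rests on assumed values of SD, k and d, on a true difference exactly at the margin, and on selective exclusion in one arm; if the worst 8 of 17 deviating subjects were picked, with deviations unrelated to outcome, the figure is about 5.2%.

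The conclusion is limited to visible text. It would need another look if the unredacted documents showed that drafts before lock carry true treatment codes and that the PP list is settled after they are reviewed.
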